#### 7. STUDY SUBJECTS

#### 7.1. Disposition of Subjects

A summary of the reasons why subjects were screened but not randomized will be presented overall in Table 1 and by site in Table 2 (Appendix 1). The disposition of subjects in the study will be tabulated by study group (Table 3 for Part A and Table 4 for Part B, Appendix 1) and by site (Table 5 for Part A and Table 6 for Part B, Appendix 1). The tables will display the total number and percentage of subjects screened, randomized, received the first administration, received the second administration, received the third administration, terminated from study follow-up, and completed the protocol.

The number of subjects included in each analysis population, and the number meeting each population exclusion criterion, will be presented in Table 7 for Part A and in Table 8 for Part B (Appendix 1).

A flowchart showing the disposition of study subjects, adapted from the CONSORT Statement [3] will be included (Figure 1 for Part A and Figure 2 for Part B, Appendix 2). This figure will present the number of subjects screened, randomized, vaccinated, and included in the mITT and PP analysis populations by study group.

A listing of subjects who discontinued dosing or terminated from study follow-up and the reason will be included in Listing 1 and Listing 2 (Appendix 3).

A listing of subjects who were unblinded during study follow-up will be included in Listing 4.

#### 7.2. **Protocol Deviations**

A summary of subject-specific protocol deviations will be presented by the reason for the deviation and the deviation category for all enrolled subjects (Table 9 for Part A, Table 10 for Part B, Table 11 for Screening Segment, Appendix 1). Deviations will be reviewed for possible subject exclusion from the per protocol population including those defined in Section 6.3. All subjectspecific protocol deviations, non-subject-specific protocol deviations, and unanticipated problem reports will be included in in data listings (Listing 3, Listing 4, Listing 5, Listing 6, Listing 7, Appendix 3).

#### 8. SAFETY EVALUATION

#### 8.1. Demographic and Other Baseline Characteristics

Summaries of age, gender, ethnicity, race, and language will be presented by study group for all enrolled subjects, the mITT population, and the ITT population (Table 13 - Table 14, for **Part A** and **Table 15 - Table 16, Part B, Appendix 1**), and by site for all enrolled subjects (Table 17 for **Part A** and **Table 18** for **Part B, Appendix 1**).

Ethnicity is self-reported by subjects as Mexican, Mexican-American, or Chicano/a; Puerto Rican; Cuban; Another Hispanic, Latinola, or Spanish origin; Not of Hispanic, Latinola or Spanish Origin; Unknown/Not Reported. Ethnicity will be summarized as categories of Any Hispanic, Latinola, or Spanish Origin, or Not of Hispanic, Latinola or Spanish Background.

In accordance with NIH reporting policy, subjects may self-designate as belonging to more than one race or may refuse to identify a race, the latter reflected in the CRF as "No" to each racial option. The race categories collected on the eCRF: White; Black or African American; American Indian or Alaskan Native; Asian Indian; Chinese; Filipino; Japanese; Korean; Vietnamese; Other Asian; Native Hawaiian; Guamanian or Chamorro; Samoan; Other Pacific Islander. Race may also be presented with categories aggregated such that any categories reported by <5% of subjects are reported as "Other".

Individual subject listings will be presented for all demographics (Listing 10 - Listing 11, Appendix 3).

#### 8.1.1. Concurrent Illnesses and Medical Conditions

All current illnesses and past or pre-existing medical conditions will be MedDRA coded using MedDRA dictionary version 20.0 or higher.

Summaries of subjects' pre-existing medical conditions will be tabulated by system organ class (SOC) and preferred term (PT) (Table 19 for **Part A** and Table 20 for **Part B**, **Appendix 1**).

Individual subject listings will be presented for all medical conditions (Listing 12 - Listing 13, Appendix 3).

#### 8.1.2. **Prior and Concomitant Therapy**

Only routine prescription medications will be entered in the database at the time of study randomization. All approved vaccinations for routine health care will be entered in the database throughout the study. Concomitant medications will be updated in the study database if there is an occurrence of an AE that requires expedited reporting or development of a new chronic medical condition that requires ongoing medical management. Otherwise, concomitant medications taken throughout the study will be recorded in the subject's chart, including any medication taking for DENV infection.

Individual subject listings will be presented for all concomitant medications (Listing 38 - Listing 39, Appendix 3).

# 8.2. Measurements of Treatment Compliance

In both parts of the study, all subjects are to receive 3 doses of study product administered in the clinic. The number of doses of study product administered to subjects will be presented by study group and by site as part of the subject disposition table as described in Section 7.1.

#### 8.3. Adverse Events

When calculating the incidence of AEs (i.e., on a per subject basis), each subject will only be counted once and any repetitions of AEs within a subject will be ignored.

#### 8.3.1. Solicited Events and Symptoms

Solicited AEs will be recorded in the study database separately with data collection on the day of administration and for 7 days after each product administration, graded on a scale of 0 (none), 1 (mild), 2 (moderate) and 3 (severe), without the collection of attribution assessments. The solicited signs and symptoms on the diary card will include the following parameters: malaise (unusually tired/feeling unwell), myalgia (muscles aches (other than at injection sites), headache, chills, nausea, joint pain, and pain/tenderness at the injection sites. Subjects will also record the highest measured temperature per day and measurement per day of the largest diameter for redness and swelling at the injection sites, if applicable. Subjects are instructed to record the greatest local symptoms or measurement when evaluating multiple injection sites. Subjects will be provided with devices to measure temperature and diameter.

The number and percentage of subjects reporting at least one solicited event of any severity following any administration will be summarized for each solicited symptom, any systemic symptom, any local symptom, and any solicited symptom. The denominator is the number of subjects in the Safety Analysis Population with non-missing data for the symptom being summarized. The 95% CI along with p-values from a Chi-square test comparing treatment groups will be presented (Table 60 for **Part A** and Table 61 for **Part B**, **Appendix 1**). In cases where there is a small sample size (e.g. Part A), Fisher's exact 2-tailed test will be presented.

For each type of reactogenicity sign and symptom, the maximum severity (none, mild, moderate, severe, or missing) reported on Day 0 through Day 7 after each administration will be summarized. Similarly, the maximum severity across all systemic events and across all local events will be summarized. The number and percentage of subjects reporting each type of event, any systemic event, and any local event will be summarized by the maximum severity for each study group separately for each administration and over all administrations. (Table 62 for **Part A** and Table 63 for **Part B**, **Appendix 1**).

The number of subjects reporting each type of solicited adverse event will be summarized for each day post administration by study group for each administration graphically in a bar chart (Figure 45 and Figure 47 for Part A and Figure 46 and Figure 48 for Part B, Appendix 2).

Solicited adverse events reported for each subject who reported at least one mild or greater event will be presented in Listing 22 - Listing 23 for systemic adverse events and Listing 24 - Listing 25 for local adverse events, **Appendix 3**.

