Regarding product administration, maximum solicited local reactogenicity in the 7 days after administration was reported as none by 9 of 90 (10.0%) subjects, mild by 55 (61.1%) subjects, and moderate by 26 (28.9%) subjects. Mild or moderate pain at the injection site was the most common symptom after product administration, reported by 81 of 90 (90.0%) subjects. Maximum solicited systemic reactogenicity in the 7 days after product administration was reported as none by 38 (42.2%), mild by 40 (44.4%), moderate by 11 (12.2%), and severe by 1 (1.1%) subject. Mild or moderate headache (37, 41.1%), malaise (33, 36.7%, which includes 1 severe event), and myalgia (22, 24.4%) were the most common symptoms reported by subjects after product administration.

VRC 705 Part B: As of July 24, 2018, 1058 subjects have randomized and received at least one product administration with ZIKVwt DNA or PBS by PharmaJet. There have been no SAEs related to study product in this part of the study. Six (6) SAEs (including: seizure, cholelithiasis, ectopic pregnancy, depression, depressive episode, and rhabdomyolysis) were reported as unrelated to study product. Regarding product administration, maximum solicited local reactogenicity in the 7 days after administration was reported as none by 354 of 905 (39.1%) subjects, mild by 411 (45.4%) subjects, moderate by 137 (15.1%) subjects, and severe by 1 (0.1%) subject. Mild or moderate pain at the injection site was the most common symptom after product administration reported by 543 (60.0%) subjects, and as severe by 1 (0.1%) subject. Maximum solicited systemic reactogenicity in the 7 days after product administration was reported as none by 425 (47.0%), mild by 338 (37.3%), moderate by 129 (14.3%), and severe by

11 (1.2%). Mild or moderate headache (312, 34.5%), malaise (275, 30.4%), and myalgia (236, 26.1%) were the most common symptoms reported by subjects after product administration.

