# 6.3. Sample Size and Accrual

# 6.3.1. Sample Size Considerations: Part A

**Part A** of the study targets healthy adults (age 18-35). Since the risk of GBS has been shown to increase with age, the study population excludes those who might be at higher perceived risk for GBS [54-56]. Ninety subjects will be randomized 1:1:1 to three vaccination arms. The sample size decision is based on the evaluation of vaccine safety and immunogenicity. Accrual up to 100 subjects is permitted if additional subjects are needed for safety and immunogenicity evaluations.

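### SAP 8.3.1 tests solicited reactogenicity between groups only as any versus none; for Part A local symptoms, where 81 of 90 subjects report one, that test is nearly uninformative and an ordinal test should be added

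*Combined protocol and SAP*

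**What the plan says.** SAP 8.3.1 grades each solicited event none, mild, moderate or severe and then sets out two summaries.

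- **Incidence (Tables 60 and 61).** "The number and percentage of subjects reporting at least one solicited event of any severity following any administration will be summarized" for each symptom, any systemic, any local and any symptom. The test belongs to this summary: "The 95% CI along with p-values from a Chi-square test comparing treatment groups will be presented". For small samples, with Part A as the example, Fisher's "exact 2-tailed test will be presented". The Table 60 shell has three pairwise p-value columns.
- **Severity (Tables 62 and 63).** Subjects with each type of event, any systemic and any local "will be summarized by the maximum severity for each study group separately for each administration and over all administrations". No test is named, and the Table 62 shell has no interval or p-value column.

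On size, Protocol 6.3.1 says: "Ninety subjects will be randomized 1:1:1 to three vaccination arms", so 30 per group. On Part A results, Protocol 1.4 says: "maximum solicited local reactogenicity in the 7 days after administration was reported as none by 9 of 90 (10.0%) subjects". Of the other 81, 55 (61.1%) were mild, 26 (28.9%) moderate and none severe. Injection-site pain alone was also reported by 81 of 90.

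**The concern.** The outcome is ordered, and the only tested version cuts it where almost everyone is on the same side. In Part A local symptoms, nine subjects are below the cut. The 55 to 26 split between mild and moderate, where most of the variation lies, contributes nothing to the p-value. Two regimens could differ clearly in how strong the local reactions are and produce identical entries in the tested table.

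Tolerability at 4 mg and at 8 mg makes up the Part A primary objectives (Protocol 3.1), and the SAP itself chose to print pairwise p-values beside those rows. A large p-value for any local symptom could be read as equal local tolerability when the test could hardly have shown otherwise. SAP 8.6 warns against that reading for laboratory data; 8.3.1 carries no such sentence.

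**Working it through.** **Inputs.** Part A: 30 per group (Protocol 6.3.1); local severity 9/55/26/0 and systemic severity 38/40/11/1 of 90 (Protocol 1.4). Part B: 1200 per arm; local severity 354/411/137/1 with arms pooled (Protocol 1.4). Assumptions: two-sided 5% level, because none is stated for these tests (Table 7 uses it); effect sizes, because the documents give no severities by group.

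**1. The plan's own figures.** Table 3, 0/30: upper limit = 1 − 0.025^(1/30) = 0.116, as printed. Table 7, 1200 per group, 25% v 30.11%: pooled SE = √(2 × 0.27555 × 0.72445/1200) = 0.01824; unpooled SE = √((0.25 × 0.75 + 0.3011 × 0.6989)/1200) = 0.01821; z = (0.0511 − 1.96 × 0.01824)/0.01821 = 0.84, so power is 80%, as stated. No power is stated for the Part A solicited comparisons.

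**2. What Fisher needs at 30 v 30.** When one group has no non-reporters and the other has k, p = 2·C(30,k)/C(60,k).
- k = 5: 2 × 142,506/5,461,512 = 0.052
- k = 6: 2 × 593,775/50,063,860 = 0.024
- 7 v 1 gives 0.052; 8 v 1 gives 0.026

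With nine non-reporters across three groups, a pairwise p ≤ 0.05 needs at least six against none, or eight against one. Full enumeration at 90% v 90% gives a true size of 0.9%. Power is 10% for 80% v 90% and 7% for 90% v 100%.

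**3. Same data, two tests.** Shift the observed local distribution symmetrically: logit P(Y ≤ j) ± ½·log(OR). For OR 3, logit(0.10) = −2.197 and ½·log 3 = 0.549, so none is 16.1% v 6.0%. Logit(0.711) = 0.901, so moderate is 19.0% v 41.3%. Fisher power is enumerated exactly; Wilcoxon is tie-corrected and simulated.

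| Part A local | Fisher, any v none | Wilcoxon on grade |
|---|---|---|
| No difference | 0.9% | 4.9% |
| OR 2 | 4% | 26% |
| OR 3 | 10% | 55% |
| OR 4 | 17% | 75% |
| Moderate 20% v 45%, any 90% in both | 0.9% | 41% |

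I also simulated the exact conditional Wilcoxon (8,000 trials per scenario). It costs two or three points: 25%, 52% and 72% for OR 2 to 4, 39% for the severity-only shift, size 3.7%.

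**4. Where the ceiling stops.** In Part A, any systemic symptom is 52/90 = 57.8%. At OR 3, Fisher has 44% and Wilcoxon 60%. In Part B local symptoms, at OR 1.2, 1.25 and 1.3, chi-square has about 59%, 76% and 88% and Wilcoxon about 66%, 82% and 93%.

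**5. Where the order reverses.** In Part B, if vaccine adds only mild local reactions (assumed none 42% v 36%, moderate 14.9% in both), chi-square has about 86% and Wilcoxon about 66%. In Part A systemic symptoms with a mild-only increase (assumed none 60% v 25%, moderate or severe unchanged), Fisher has 72% and Wilcoxon about 62%.

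**The case against.** Several points on the other side are sound.

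- **Severity is not discarded.** It is tabulated by group, by administration and overall, charted by day (Figures 45 to 48) and listed. A mild-to-moderate shift would be visible in Table 62; it would only lack a p-value. A reader might infer that severity is never compared, but the documents support only that it is never tested.
- **No design target fails.** The Part A objectives are two non-comparative statements, its safety precision is framed within group (Tables 2 and 3), and no between-regimen safety power is claimed. What is lost is information.
- **Little rides on it now.** Part A vaccination ended in October 2017, the Part B regimen has been chosen, and SAP version 1.0 is dated November 2019. Part A is open-label and its pooled severities are known, so a new test there comes after the data.
- **The comparison can favour the ordinal test.** Proportional-odds and severity-only shifts both suit Wilcoxon, and part of the gap is Fisher's conservatism (0.9% size). Step 5 shows that mild-only increases go the other way. With an even starker severity-only shift (moderate 15% v 50%), Fisher on moderate-or-worse has 78%, against 68% for Wilcoxon.

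Together these rule out replacing the planned tests and require an open label on any addition. They do not rescue the Part A local p-values: an ordinal test would have to lose most of its advantage before any-versus-none at 90% incidence became the better guide.

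**Conclusion.** The concern holds in a limited form. Any-versus-none is the only formal between-group comparison of solicited events. For Part A any local symptom, injection-site pain and the any-symptom row (necessarily at least 90%), it is close to uninformative: about 1% size and 4 to 17% power for odds ratios of 2 to 4, where an ordinal test on the same data has about 26 to 75%.

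A reader might go further and conclude that the solicited-event comparisons cannot separate the regimens at all, or that Part B is affected in the same way. Neither follows. Part A systemic symptoms are limited mainly by 30 per group, and in Part B the two tests differ by only about 4 to 7 points under proportional odds.

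The 81 of 90 and the severity split come from Protocol 1.4, which calls the data preliminary. The odds ratios and severity shifts are assumed and shown as a range. The Fisher thresholds in step 2 rest on no effect-size assumption.

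**What to change.** Amend SAP 8.3.1 as follows.

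1. Keep the any-severity tests, percentages and exact intervals in Tables 60 and 61. Correct the Table 60 shell, whose p-value heading says chi-square where the text calls for Fisher in Part A.
2. Add to Table 62 pairwise exact Wilcoxon rank-sum (linear-by-linear) p-values on maximum severity 0 to 3 over all administrations, for each solicited symptom, any local and any systemic. A row-mean-score test in Table 63 is optional.
3. Label these as supplementary, unadjusted comparisons introduced by amendment.
4. Add a sentence to 8.3.1, parallel to the one in 8.6, that a non-significant result is not evidence of no difference.

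The cost is SAP wording and one further procedure call on data already tabulated. There will be more unadjusted p-values, in a plan that makes no multiplicity adjustment. The ordinal p-value also has no single risk difference attached, so it has to be read beside the severity percentages.

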#### Part B:

- To evaluate the safety and tolerability of VRC-ZKADNA090-00-VP in healthy adults and adolescents when administered IM at a dose of 4 mg by needle-free injection device compared to placebo.
- To evaluate the efficacy of VRC-ZKADNA090-00-VP by comparing incidence rates of virologic ZIKV cases in vaccine and placebo recipients.

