# 6.3.2. Sample Size Considerations: Part B

**Part B** of the study targets healthy adults and adolescents ages 15 to 35 years who reside in ZIKV endemic or potential endemic regions. This age range is considered to be the range of the highest reproductive potential and therefore, this age group will likely be the initial target for a successful ZIKV vaccine. Additionally, the risk of GBS has been shown to increase with age, so

this study population excludes those who might be at higher perceived risk for GBS [54-56]. Randomization at each study site will equally allocate subjects to vaccine or placebo schedules. The randomization plan does not include provisions for replacing subjects with incomplete product administration or visit schedules.

A total of 2400 subjects will be randomized 1:1 to receive either the study vaccine or placebo. The study sample size was determined primarily based on the evaluation of vaccine efficacy (VE). The study also has ample sample size for detecting AEs, therefore meeting the primary endpoints.

To detect a VE of 61%, the trial aims to achieve 90 cases of naturally acquired virologic ZIKV infection within 2 to 3 years. If it appears this target is unlikely to be met, the study may be expanded to achieve this target. Prior to the completion of randomization, the combined vaccine and placebo incidence rate of subclinical ZIKV cases will be calculated. At each site, the blinded site-specific baseline seropositivity rate may be calculated and used to adjust the needed sample size and to aid in allocation of enrollment slots. Both types of rates will be used to help decide if the enrollment should be extended to allow for the target to be achieved. For planning purposes, we will allow for a total sample size of up to 15,000. Such a sample size could achieve our target number of virologic ZIKV cases within 3 years, assuming full accrual within 12 months, even if the placebo incidence rate is as low as 0.50% and the seropositive rate is as high as 30% among enrollees.

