# Table 6: Probability of Observing Safety Events within a Group (n=1200)

Table 7 provides the minimum detectable difference by two-sided chi-square test between the vaccine and placebo groups over a range of possible event rates and sample sizes as follows: 1200 samples per group, 960 samples per group to account for 20% early drop out, 480 and 240 samples per group for comparisons within a stratum defined by baseline ZIKV status.

Table 7:Minimum Detectable Difference in Event Rate Assuming Type I Two-Tail
Error Rate of 5%

Sample size	Event rate	Detectable wit	th 80% power	Detectable wi	th 90% power
group (#) (in placebo) (%)		Difference (%)	Event rate (in vaccine) (%)	Difference (%)	Event rate (in vaccine) (%)
	0.1	0.81	0.91	1.04	1.14
	0.5	1.19	1.69	1.46	1.96
1200	1.0	1.50	2.50	1.80	2.80
1200	5.0	2.80	7.80	3.29	8.29
	10.0	3.69	13.69	4.32	14.32
	25.0	5.11	30.11	5.93	30.93
	0.1	0.98	1.08	1.26	1.36
	0.5	1.39	1.89	1.71	2.21
960	1.0	1.73	2.73	2.09	3.09
	5.0	3.17	8.17	3.74	8.74
	10.0	4.16	14.16	4.88	14.88
	25.0	5.73	30.73	6.66	31.66
400	0.1	1.79	1.89	2.33	2.43
	0.5	2.30	2.80	2.88	3.38
	1.0	2.75	3.75	3.38	4.38
480	5.0	4.72	9.72	5.60	10.60
	10.0	6.08	16.08	7.15	17.15
	25.0	8.20	33.20	9.55	34.55
	0.1	3.38	3.48	4.43	4.53
	0.5	3.97	4.47	5.04	5.54
240	1.0	4.54	5.54	5.65	6.65
240	5.0	7.14	12.14	8.55	13.55
	10.0	8.98	18.98	10.61	20.61
	25.0	11.79	36.79	13.73	38.73

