Any SAEs reported before the first study product administration receipt at Visit 02 will be listed in Table 72, Table 78, Table 84, Appendix 1. All other tables and figures of unsolicited AEs will include only AEs reported following the first study product administration.

The number and proportion of subjects reporting at least one unsolicited adverse event will be summarized by MedDRA SOC and PT by study group for each study product administration and

over all study product administrations. Denominators for percentages are the number of subjects in the Safety Analysis Population who received the administration being summarized (Table 73, Table 74, Table 75 for Part A and Table 76, Table 77 for Part B, Appendix 1). For each MedDRA system organ class and preferred term a 95% CI will be presented, along with the p-value for the comparison of study groups from a Fisher's exact test for Part A and a Chi-square test for Part B (Table 64, Table 65, Table 66, Table 67 for Part A and Table 68, Table 69, Table 70, Table 71 for Part B, Appendix 1).

The following summaries for unsolicited adverse events will be presented by MedDRA system organ class, preferred term for each administration and overall administrations, for all subjects:

- Proportion of subjects reporting adverse events by severity (Table 64 through Table 78, Appendix 1);
- Proportion of subjects reporting related adverse events by severity (Table 79 through Table 84, Appendix 1);
- Proportion of subjects reporting related adverse events by dose (Table 85 through Table 89, Appendix 1);
- Number of adverse events by dose (Table 90 through Table 94, Appendix 1);
- Number and proportion of subjects experiencing adverse events above 5% frequency threshold by MedDRA SOC and PT (Table 95 Table 96, Appendix 1);
- Bar chart of the proportion of subjects reporting any adverse events by severity (Figure 49 Figure 50, Appendix 2);
- Bar chart of adverse events by severity and MedDRA SOC for SOCs reported by 5% or more of subjects (Figure 53 Figure 54, Appendix 2);
- Bar chart of adverse events by relationship to study product (Figure 51 Figure 52, Appendix 2);

Unsolicited AEs by subject will be presented in Listing 26 through Listing 28, Appendix 3.

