# 8.4.3. Confirmed Cases of DENV (Part B)

For **Part B**, confirmed cases of DENV will be recorded on an AE Form throughout the full duration of the study. The incidence of DENV will be summarized as the number and percentage of subjects tabulated by treatment arm overall and stratified by baseline ZIKV Status. 95% CIs will be included along with p-values from Chi-Square test (Table 107, Appendix 1).

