# 2) For laboratory parameters with three categories: Low, Normal and High (Ordinal response)

- a. For each parameter the shift table displays the number of subjects who are categorized as low, normal, or high at baseline cross tabulated with low, normal or high results at the post-vaccination visit.
- b. A GEE model for the ordinal responses above is fitted and used for parameter estimation
  - Observation  $(Y_{ij}, X_{ij})$  for each subject i = 1, ..., n at time point j = 1, ..., J.  $Y_{ij} = (y_{ij1}, y_{ij2})$  is the ordinal response variable with 3 ordered categories;
  - Cumulative probability pijk = Pr(yijk = 1: in lower k category) = Pr(Yij ≤ k), k = 1,2;
  - Proportional Odds model  $\begin{cases} g(p_{ij1}) = \mu_1 + X'_{ij}\beta \\ g(p_{ij2}) = \mu_2 + X'_{ij}\beta \end{cases}$  using the logit link;
  - $X'_{ij}\beta = -\beta_1 t_{ij} + \beta_2 group_{ij} + \beta_3 t_{ij} * group_{ij}$
  - GEE:  $\sum_{i=1}^{n} \left(\frac{\partial P_i}{\partial \beta}\right) V_i^{-1}(\alpha) (Y_i P_i) = 0$  where  $P_i = E(Y_i) V_i(\alpha)$  is the working covariance matrix;
  - Output: estimates of two intercepts from the two fitted logistic models; point estimates and 95% CI for the individual levels of the GROUP, TIME and GROUP\*TIME variables, and Type-3 SAS output for the parameter significance (chi-Square test);

The study is not powered to detect differences by study group, therefore the absence of statistically significant differences should not be interpreted as no such differences exist.

Individual clinical laboratory results will be presented for subjects with abnormal results of Grade 2 or higher for at least one parameter from at least one visit, including planned parameters collected at scheduled visits as well as any other parameters collected, and any results for unscheduled visits in Table 167 for **Part A** and Table 168 for **Part B**, **Appendix 1**.

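### Part B plans no vaccine-versus-placebo effect estimate with a confidence interval for clinical adverse events, although its primary safety objective is a comparison with placebo

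*Combined protocol and SAP*

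**What the plan says.** Protocol 3.1 sets the Part B safety objective as safety and tolerability "when administered IM at a dose of 4 mg by needle-free injection device compared to placebo". Allocation is 1:1 among 2400 subjects (Protocol 6.3.2).

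The planned statistics for clinical events in Part B are:

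- **Solicited events (SAP 8.3.1, Table 61):** "The 95% CI along with p-values from a Chi-square test comparing treatment groups will be presented".
- **Unsolicited AEs (SAP 8.3.2, Tables 68-71):** by system organ class and preferred term, "a 95% CI will be presented, along with the p-value for the comparison of study groups"; in Part B the test is chi-square.
- **Confirmed DENV (SAP 8.4.3, Table 107):** "95% CIs will be included along with p-values from Chi-Square test".
- **SAEs (SAP 8.4.1, Table 98):** number and proportion. The shell has no interval and no p-value column.
- **New chronic medical conditions (SAP 8.4.2):** a listing, plus a count-and-percentage row in Table 97.

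SAP 6.1 makes Clopper-Pearson the default interval for proportions. The shells for Tables 60, 64 and 107 place an interval under each study group, and none has a difference or ratio column. No margin, or excess risk to be ruled out, is stated.

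Two safety domains are treated differently. SAP 8.6 fits GEE models to laboratory shifts, with group estimates and, for binary parameters, an odds ratio with a 95% interval. Protocol 6.4.5 monitors harm in ZIKV cases with a nominal 95% interval for the hazard ratio.

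**The concern.** A comparative objective needs a comparative estimate. A per-arm interval describes one arm. A p-value says whether the arms are distinguishable, not how far apart they might be. For common reactogenicity the distinction is minor, because power is high. For SAEs, new chronic conditions and DENV it is the main question: with few events, a result that looks balanced, or is not significant, can coexist with a several-fold excess. The categories of greatest clinical weight get the least comparative analysis, and the reader of the planned tables is not shown what remains possible.

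**Working it through.** **Inputs.** 1200 per arm, and 960 per arm after 20% early dropout (Protocol 6.3.2.1); two-sided 5% chi-square (Table 7). The placebo event rates are assumed, from 0.25% to 2%.

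**1. Reproduce Table 7.** With d = p1 − p0 and p̄ the mean of the two rates:

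power = Φ[(d − 1.96·s0)/s1], where s0 = √(2p̄(1−p̄)/n) and s1 = √([p0(1−p0) + p1(1−p1)]/n).

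For n = 1200, p0 = 0.5%, p1 = 1.69%: s0 = 0.004249, s1 = 0.004242, and (0.0119 − 0.008327)/0.004242 = 0.842, so power = 0.80, as stated. All 48 cells of Table 7 reproduce to within 0.01 percentage point. In relative terms, 80% power needs 1.69/0.5 = 3.4-fold at 1200 per arm and 1.89/0.5 = 3.8-fold at 960. At a placebo rate of 0.1% and 1200 per arm it needs 0.91/0.1 = 9.1-fold.

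**2. Power for a doubling.** For n = 1200, 0.5% versus 1.0%: s0 = 0.003522, s1 = 0.003521, and (0.005 − 0.006903)/0.003521 = −0.541, so power = 0.294. Exact enumeration of two independent binomials with the uncorrected Pearson test gives 0.295, a miss rate of 71%. The exact miss rates are:

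| Placebo rate | Vaccine rate | Missed, 1200 per arm | Missed, 960 per arm |
|---|---|---|---|
| 0.25% | 0.5% | 85% | 87% |
| 0.5% | 1.0% | 71% | 77% |
| 1% | 2% | 47% | 55% |
| 2% | 4% | 17% | 26% |

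**3. Where the SAE rate might lie.** Protocol 1.4 reports 6 SAEs among 1058 Part B subjects at 24 July 2018, so 6/1058 = 0.57% if each was in a different subject. At that rate a doubling would be missed 67% (73%) of the time. The count pools both arms, is labelled preliminary, and was taken about a year after accrual began, against 96 weeks of planned follow-up. It is one point in the range, not an estimate of the final placebo rate.

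**4. What an interval would add (illustrative counts).** Take 13/1200 on vaccine (1.08%) and 7/1200 on placebo (0.58%). The pooled rate is 20/2400 = 0.83%, the standard error √(2 × 0.00833 × 0.99167/1200) = 0.00371, z = 0.0050/0.00371 = 1.35 and p = 0.18. The score 95% interval for the difference is −0.25 to +1.33 percentage points. For the risk ratio of 13/7 = 1.86 it is 0.77 to 4.51. The planned format for an unsolicited AE or DENV would show the two percentages, two separate intervals and p = 0.18. For an SAE it would show the two counts and percentages. Neither shows that an excess of 1.3 percentage points, or a 4.5-fold risk, is still compatible with the data.

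**The case against.** Several stronger readings are tempting, and the documents do not support them.

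- **That a chi-square p-value is the only between-arm safety statistic in Part B.** It is not. The laboratory GEE estimates and the ZIKV hazard-ratio interval are between-arm estimates, and Protocol 6.2.1 lists both domains as safety parameters. Protocol 6.4 also names logistic regression among its general methods. The gap is confined to clinical adverse events and DENV.
- **That non-significance will be taken as safety.** No such rule is written. SAP 8.6 warns against that inference, although only in the laboratory section. SAEs have no p-value to misread.
- **That a doubled SAE rate would be missed two times in three.** That holds only near the interim 0.57%, and it describes a test the SAP does not plan for SAEs.
- **That the two documents contradict each other on power.** Protocol 6.3.2 says "The study also has ample sample size for detecting AEs, therefore meeting the primary endpoints" and SAP 8.6 says "The study is not powered to detect differences by study group". The first concerns observing events, which Table 6 supports; the second closes the laboratory models. Table 7 already discloses the limited comparative power, so that Protocol sentence need not be edited for this point.

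It can also be said that arm-level counts in Tables 97, 98 and 107 let any reader compute a difference and interval, that SAEs are covered by pause rules, DSMB review, listings and narratives, and that an added column creates no new information. All of this is true. The safeguards do not quantify an excess over placebo, however, and a primary objective should not depend on readers doing their own calculation. The sponsor already supplies such intervals for laboratory abnormalities and ZIKV harm.

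**Conclusion.** The concern holds in a limited form. For clinical adverse events and DENV in Part B, no planned table gives a between-arm effect size with a confidence interval, and SAEs and new chronic conditions have no between-arm statistic at all. It would be too much to conclude that the trial cannot address its primary safety objective: the data will be collected and the counts shown by arm. What is missing is the estimate that states the comparison.

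The size depends on the event rate. The several-fold detectable ratios for rare events follow from the sponsor's own Table 7. The miss rates for a doubling assume placebo rates of 0.25% to 2%, equal arms, independent subjects and the uncorrected chi-square; the 960-per-arm figures treat dropouts as contributing nothing. Common solicited events are little affected: at a 25% placebo rate Table 7 gives a detectable difference of 5.11 points. This is an inexpensive reporting improvement that should be made. It is not a flaw in the trial's conduct or size.

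**What to change.** 1. In SAP 8.3.2, 8.4.1, 8.4.2 and 8.4.3, add the vaccine-minus-placebo risk difference with a two-sided 95% score (Miettinen-Nurminen) interval for: any unsolicited AE, any related unsolicited AE, Grade 3 or higher AE (the severe category, since SAP 8.3.2 maps Grades 4 and 5 to Grade 3), SAE, new chronic medical condition and confirmed DENV. Place it in Tables 68-71, 97, 98 and 107. Adding it for any solicited event (Table 61) is optional.
2. State that the comparative safety conclusion will be worded from these intervals, in particular the upper limit, and not from whether p exceeds 0.05.
3. Move or repeat the SAP 8.6 caution on non-significance in SAP 8.3 so that it covers all safety endpoints.
4. State that the intervals are descriptive and unadjusted for multiplicity, in line with Protocol 6.4, which plans no adjustment.

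The cost is a few extra table columns and some SAP wording. It needs no new data, subjects or decision rule.
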